# 11.5.2. Handling of Missing Data

Element	Reporting Detail
General	Missing data occurs when any requested data is not provided, leading to blank fields on the collection instrument:
	
 
These data will be indicated by the use of a "blank" in participant listing displays.
 
Unless all data for a specific visit are missing in which case the data is excluded from the table.
 

	
 
Answers such as "Not applicable" and "Not evaluable" are not considered to be missing data and should be displayed as such.
 

Outliers	Any participants excluded from the summaries and/or statistical analyses will be documented along with the reason for exclusion in the clinical study report.

# 11.5.2.1. Handling of Missing and Partial Dates

Element	Reporting Detail				
General	Partial dates will be displayed as captured in participant listing displays.				
Adverse Events	
 
The eCRF allows for the possibility of partial dates (i.e., only month and year) to be recorded for AE start and end dates; that is, the day of the month may be missing. In such a case, the following conventions will be applied for calculating the time to onset and the duration of the event:         
 
Missing Start Day: First of the month will be used unless this is before the start date of study treatment; in this case the study treatment start date will be used and hence the event is considered On-treatment as per Appendix 2: Study Phases and Treatment Emergent Adverse Events.
 
Missing Stop Day: Last day of the month will be used, unless this is after the stop date of study treatment; in this case the study treatment stop date will be used.
 
 
 
Completely missing start or end dates will remain missing, with no imputation applied.
 
				
Concomitant	Consequently, time to onset and duration of such events will be missing.      Partial dates for any concomitant medications recorded in the eCRF will be imputed.				
Medications	
 
Partial dates for any concontraint medications recorded in the eCRP will be imputed using the following convention:         
 
If the partial date is a start date, a '01' will be used for the day and 'Jan' will be used for the month
 
If the partial date is a stop date, a '28/29/30/31' will be used for the day (dependent on the month and year) and 'Dec' will be used for the month.
 
 
 
The recorded partial date will be displayed in listings.
 
				

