# 11. APPENDICES

# 11.1. Appendix 1: Schedule of Activities

# 11.1.1. Protocol Defined Schedule of Events

# **Screening Visit**

Procedure	Screening (up to 28 days before Day -4)
Outpatient visit	X
Informed consent	X
Inclusion and exclusion criteria	X
Demography	X
Full physical examination including height and weight 	X
Laboratory assessments (hematology, chemistry, urinalysis)	X
12-lead electrocardiogram (ECG)	X
Vital sign measurements	X
Medication/drug/alcohol history	X
Past and current medical conditions	X
Columbia Suicide Severity Rating Scale (C-SSRS)	X
Serum pregnancy test	X
Drug, alcohol, and cotinine screen	X
Human immunodeficiency virus (HIV), Hepatitis B and C screening	X

<sup>1. A full physical examination will include at a minimum, assessments of the skin, cardiovascular, respiratory, gastrointestinal (GI), and neurological systems.

Table 2 Time and Events Table

Procedure	Check-in		Run-ir	1				_	Tre	eatmen	t					Wash	nout 1		Notes
	D -4	D -3	D -2	D -1	D 1	D 2-9	D 10 	D 11	D 12	D 13	D 14-18	D 19	D 20	D 21	D 22	D 23	D 24 	D 25	
Admit to clinic	Х																		
Discharge from clinic																		Χ	
Brief physical examination	Х						х										Х		A brief physical examination will include, at a minimum, assessments of the skin, lungs, cardiovascular system, and abdomen (liver and spleen.
Vital signs	Х				Х		х	Х			D15			Х			Х		Obtained before dosing, where applicable. Blood pressure and pulse will be measured in triplicate when they occur at the same time point as clinical laboratory assessments.
12-lead ECG	Х				Х		Х	х			D15			Х			Х		On Day 11, triplicate ECGs will be taken before dosing. On Day 11, single ECGs will be taken at 2, 4, and 6 hours after dosing. On Day 15, single ECGs will be taken at 2, 4, and 6 hours after dosing. Single ECGs will be taken on other scheduled days.

Procedure	Check-in	ı	Run-ir	1					Tre	eatmen	t					Wash	nout 1		Notes
	D -4	D -3	D -2	D -1	D 1	D 2-9	D 10 	D 11	D 12	D 13	D 14-18	D 19	D 20	D 21	D 22	D 23	D 24 	D 25	
Drug, alcohol, and cotinine screen	Х																		See Protocol Appendix 2 for specific tests to be performed.
Laboratory assessments (hematology, chemistry, urinalysis tests)	Х				Х		Х							х			х		See Protocol Appendix 2 for specific tests to be performed. Taken before dosing, where applicable.
Pregnancy test	Х			Χ			Χ										Х		
Genetic sample (optional)	Х																		
C-SSRS								Χ						Х					

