# 11.2. Appendix 2: Study Phases and Treatment Emergent Adverse Events

# 11.2.1. Study Phases

Assessments and events will be classified according to the time of occurrence relative to study treatment start date(/time) and stop date(/time).

Study Phase	Definition
Pre-Treatment	Date and Time ≤ Study Treatment Start Date and Time
On-Treatment	Study Treatment Start Date and Time < Date and Time ≤ Study Treatment Stop Date and Time + 5 days
Post-Treatment	Date and Time > Study Treatment Stop Date and Time + 5 days

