# 11.2.2. Treatment Emergent Flag for Adverse Events

Flag	Definition
Treatment Emergent	• If AE onset date and time is on or after treatment start date and time & on or before treatment stop date and time + 5 days.
	
 
Study Treatment Start Date and Time ≤ AE Start Date and Time ≤ Study Treatment Stop Date and Time + 5 days.
 

	
 
If the AE onset date is completely missing, the AE is considered as treatment emergent.
 

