#### NOTES:

- If the study treatment stop date is missing, then the AE will be considered to be On-Treatment.
- Please refer to Appendix 5: Reporting Standards for Missing Data for handling of missing and partial dates for adverse events. Use the rules in this table if the adverse event onset date is completely missing.

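### The missing-start-day rule for adverse events has no same-month condition and no stop-date check, so an event known to have begun before first dose can be classed as On-treatment

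*SAP*

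**What the plan says.** Section 11.5.2.1 (Adverse Events) applies when the start date is partial: "that is, the day of the month may be missing". The start is set to the 1st of the recorded month, with one exception: "unless this is before the start date of study treatment; in this case the study treatment start date will be used and hence". The SAP's conclusion from this, citing Appendix 2, is that such an event belongs to the On-treatment phase. For a partial end date the rule is "Missing Stop Day: Last day of the month will be used, unless this is after the stop date of study treatment", in which case the treatment stop date is used. Neither rule compares the imputed start with the end of the event.

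Appendix 2 then classifies the date. The phase table in section 11.2.1 defines Pre-Treatment as "Date and Time ≤ Study Treatment Start Date and Time". The flag in section 11.2.2 defines treatment-emergent as "Study Treatment Start Date and Time ≤ AE Start Date and Time ≤ Study Treatment Stop Date and Time + 5 days". The notes to 11.2.2 send partial dates to Appendix 5 and add no limiting condition.

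**The concern.** Moving an event to first dose is a sensible conservative choice when its timing is ambiguous, that is, when it began in the month of first dose and is not known to have ended before dosing. The rule goes further. It also applies when the recorded data already settle the question: the recorded month is earlier than the month of first dose, or the recorded stop date precedes first dose. In those cases the imputation overrides known information, and an event that began before treatment is labelled On-treatment.

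Two things are at stake. One is correct classification in a small single-sequence study, where one spurious event is visible. The other is the rule's own purpose: section 11.5.2.1 says its conventions serve to calculate time to onset and duration, and a start placed after the event's end defeats that.

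**Working it through.** The SAP gives no figure to reproduce, so the check applies its rules to example dates.

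Inputs:
- Imputation rules: 11.5.2.1. Classification rules: 11.2.1 and 11.2.2.
- Portia dosing runs from Day -3 to Day 21 with no Day 0, which is 3 + 21 = 24 dosing days (Time and Events Table).
- Assumed: first dose 12 August 2019, so last dose is 23 days later (4 September) and the 5-day tail ends on 9 September.
- Assumed: duration = stop date - start date + 1.

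| Recorded start; stop | Imputed start under SAP | Treatment-emergent (11.2.2) | Duration under SAP |
|---|---|---|---|
| (a) July; 28 July | 12 Aug | yes | -15 + 1 = -14 |
| (b) July; July, imputed as 31 July | 12 Aug | yes | -12 + 1 = -11 |
| (c) July; ongoing | 12 Aug | yes | none |
| (d) August; 5 August | 12 Aug | yes | -7 + 1 = -6 |
| (e) August; ongoing | 12 Aug | yes | none |
| (f) September; ongoing | 1 Sep | yes | none |

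Cases (a) to (d) are wrong, because the recorded data place the onset before first dose. Case (e) is reasonable conservatism and case (f) is correct.

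With a same-month condition and a stop-date check:
- (a) starts 1 July, not treatment-emergent, duration 27 + 1 = 28 days.
- (b) starts 1 July, not treatment-emergent, duration 30 + 1 = 31 days.
- (c) starts 1 July, not treatment-emergent.
- (d) starts 1 August, not treatment-emergent, duration 4 + 1 = 5 days.
- (e) and (f) do not change.

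**Boundary.** In cases (a) to (e) the imputed start equals treatment start. The 11.2.1 phase table puts equality in Pre-Treatment, whereas 11.2.2 counts equality as treatment-emergent. Section 11.5.2.1 calls the event On-treatment and cites Appendix 2 for this, but the phase table in that appendix says otherwise.

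**How often a pre-dose date falls in an earlier month.** This depends on the collection window, which has to be assumed. Take start dates spread evenly over 365 days and pre-dose events uniform over the window.
- Window of 1 day (Day -4 only): 12/365 = 3.3%.
- Window of 29 days (28 days before Day -4, plus Day -4): for first dose on day d of the month, (30 - d)/29 of the lags fall earlier. This sums to 435/29 = 15 for each of eleven months and 434/29 = 14.97 for February, so (165 + 14.97)/365 = 49.3%.

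These are shares of pre-dose events with a missing start day, not shares of all events.

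**The case against.** The strongest objection is that the rule will hardly ever be triggered. Participants are admitted on Day -4 and discharged on Day 25, so a missing onset day should be rare. The Screening Visit table lists no adverse event review, and the Time and Events Table seems to start SAE review at check-in and general AE review slightly later, although its layout does not settle this. The error also over-counts rather than hides events, and listings show partial dates as captured. All of this stands, and it limits frequency. It does not make the rule right.

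A reader might infer several stronger points that the SAP does not support:
- **That about half of pre-dose partial dates are affected.** The 49% needs events to be collected uniformly over 29 days. The SAP allows "Screening (up to 28 days before Day -4") but shows no adverse event review at that visit.
- **That the main adverse event tables are inflated.** Tables 2.1 to 2.6 and 2.20 are not titled treatment-emergent, and the SAP does not say that the flag selects their content. No Appendix 9 table is titled for event duration or time to onset.
- **That the note in 11.2.2, "If the study treatment stop date is missing, then the AE will be considered to be On-Treatment", is a second fault.** A missing treatment stop date leaves only the upper bound undefined. The natural reading is that the note fills that bound and leaves the onset condition in force.

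**Conclusion.** The rule as written gives a wrong result for two kinds of event with a missing start day: those recorded in a month before the month of first dose, and those in the month of first dose with a stop date before first dose. Both are classed On-treatment and treatment-emergent, and those with a stop date before first dose get an onset after their own end. Nothing in Appendix 2 repairs this.

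The effect is likely to be very small. The share of eligible events falling in an earlier month runs from about 3% to 49% across the assumed windows, and the schedule points towards the lower end. The number of eligible events is not known and should be very few. The rules do not say whether study treatment start means Day -3 or Day 1. The fault holds under either reading; under Day -3 the affected events land on the run-in and not on the combination. The equality clash between 11.2.1 and 11.2.2 is a separate drafting inconsistency that this imputation exposes directly.

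**What to change.** Replace the missing-start-day rule in 11.5.2.1 with three branches:
1. Recorded month and year earlier than those of first dose: impute the 1st of the recorded month and classify as Pre-Treatment.
2. Recorded month and year equal to those of first dose, with the 1st before treatment start: use the treatment start date, unless the event's stop date is before first dose. In that case impute the 1st and classify as Pre-Treatment.
3. Recorded month and year later than those of first dose: keep the 1st of the month and classify by the existing Appendix 2 rules.

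The third branch must be explicit. A two-way rule that sent everything outside the month of first dose to Pre-Treatment would misclassify case (f). With onsets uniform over lags of 0 to 28 days from first dose (23 days to last dose plus 5), 12 × 14/365 = 46% of on-treatment dates fall in a later month.

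Also align 11.2.1 and 11.2.2 on an onset equal to treatment start. Optionally, add a clause that the missing-stop-date note replaces only the upper bound.

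The cost is a few sentences of SAP text and one derivation condition in the adverse event dataset. No ambiguous event loses its conservative treatment.

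### The missing-stop-day rule for adverse events is capped at the last dose with no floor, so an AE that starts after the last dose gets a stop date before its start (minor)

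*SAP*

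**What the plan says.** SAP Section 11.5.2.1 allows AE dates with the day missing and says that its conventions are "applied for calculating the time to onset and the duration of the event". For the end date the rule reads "Missing Stop Day: Last day of the month will be used, unless this is after the stop date of study treatment"; when month-end is later than that, "in this case the study treatment stop date will be used". The rule refers neither to the AE's start date nor to the month entered for its end.

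Appendix 2 sets the AE window. The treatment-emergent flag in Section 11.2.2 is "Study Treatment Start Date and Time ≤ AE Start Date and Time ≤ Study Treatment Stop Date and Time + 5 days". The On-Treatment phase in Section 11.2.1 has the same upper limit. Section 5.1 places the last dosing day at Day 21, and the schedule in Section 11.1.1 runs to Day 25.

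For a missing start day, Section 11.5.2.1 uses the first of the month unless that precedes treatment. In that event "the study treatment start date will be used and hence the event is considered On-treatment", with Appendix 2 cited as the basis. The Notes to Section 11.2.2 point the other way: "Please refer to Appendix 5: Reporting Standards for Missing Data for handling of missing and partial dates for adverse events".

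**The concern.** A cap at the last dose suits AEs that resolve during dosing. The plan deliberately also collects and counts AEs that begin after dosing has ended. For those, a date capped at the last dose lies before the event began, so the rule gives an impossible answer for duration, one of the two quantities it exists to compute. A programmer would have to publish zero or negative durations or improvise a correction that the plan does not document.

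The same cap can contradict recorded data. If the eCRF gives the month of resolution and that month is later than the month of the last dose, the imputed stop falls in a month that the site did not record.

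**Working it through.** The SAP states no figure on this point, so the rule is applied literally.

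**Inputs**
- Imputed stop = the earlier of (last day of the recorded stop month, treatment stop date): Section 11.5.2.1.
- Last dose on Day 21: Section 5.1. First dose on Day -3: schedule in Section 11.1.1.
- AE window to treatment stop + 5 days, so to Day 26: Sections 11.2.1 and 11.2.2.
- Duration = stop - start + 1 (assumed; the SAP gives no formula).

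**Step 1: the inversion is certain.** Take a complete onset date after the last dose. The last day of the stop month is on or after the true stop, which is on or after the onset, which is after the last dose. The cap therefore always applies, the imputed stop is the last dose date, and that date precedes the onset. This holds for any calendar date, any AE length, and any earlier last dose in a participant who discontinues.

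| Onset | Imputed stop | Duration |
|---|---|---|
| Day 22 | Day 21 | 21 - 22 + 1 = 0 |
| Day 23 | Day 21 | 21 - 23 + 1 = -1 |
| Day 24 | Day 21 | 21 - 24 + 1 = -2 |
| Day 25 | Day 21 | 21 - 25 + 1 = -3 |

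Onset on Day 26, the last day of the window, would give -4. Enumeration over 1,461 Day 1 dates (2019 to 2022) gave a stop before the start in 100% of cases.

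**Step 2: the recorded month can be overridden.** Suppose Day 1 is 8 August. Day 21 is then 28 August, Day 22 is 29 August and Day 25 is 1 September. An AE with onset on 29 August and an end recorded only as September gets a stop of 28 August, which is before its onset and in the wrong month. How often this happens depends on the assumptions. With equally weighted onset and end pairs and onset on Days 22 to 25, it is 9.9% if no AE ends after Day 25 and 35% if ends run to Day 40.

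**Step 3: effect of two floors.** Imputed stop = the latest of (present result, AE start date, first day of the recorded stop month). In the Step 2 example this is the latest of 28 August, 29 August and 1 September, so 1 September, with a duration of 4 days. In the enumeration for onset on Days 22 to 25, stops before the start and month overrides both fall to 0%, whether ends are limited to Day 25 or to Day 40. The mean absolute error in the stop date falls from 3.0 to 0.95 days (ends to Day 25) or from 10.7 to 6.6 days (ends to Day 40). Stops imputed for AEs that resolved on Days 11 to 21 do not change.

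**Step 4: a case that the floors alone do not settle.** Suppose the first dose (Day -3) is on 1 September and an AE is confined to Day -4, 31 August, with both days missing. The start rule moves the onset to 1 September, because 1 August precedes treatment. The stop rule gives 31 August. A floor at the imputed start would push the stop into September, against the record. This needs a first dose on the first of a month (48 of 1,461 dates, 3.3%).

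**Step 5: side note on the phase label.** Section 11.2.1 defines Pre-Treatment as "Date and Time ≤ Study Treatment Start Date and Time" and On-Treatment as "Study Treatment Start Date and Time < Date and Time ≤ Study Treatment Stop Date and Time + 5 days". A start set equal to treatment start is therefore Pre-Treatment by that table. Section 11.2.2 uses ≤ at the same boundary and flags it treatment emergent. The On-treatment label in Section 11.5.2.1 thus does not follow from the phase table that it relies on.

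**The case against.** The strongest reply is that almost nothing depends on this. Participants are confined from Day -4 to Day 25, so partial AE dates should be rare. Listings show partial dates as captured, no AE table or listing in Appendix 9 is titled for duration or phase, and the stop-day rule changes no AE count. All of that stands, and it is why the point is minor. It does not rescue a written rule that always fails for an identifiable class of events.

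Two stronger readings are tempting, and the SAP supports neither.

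First, a reader might infer from Step 5 that partially dated AEs will be assigned to the wrong phase or drop out of the treatment-emergent tables. The Notes to Section 11.2.2 send partial dates to Appendix 5, which states the On-treatment outcome itself. Compared by date, or at the dosing time, the Section 11.2.2 flag returns treatment emergent, as intended. It would fail only if midnight were attached to the imputed date, and no section assigns midnight. What is left is a ≤ against < mismatch with one phase label.

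Second, a reader might infer that the cap at last dose is itself an error, because it shortens AEs that continue past dosing. For onsets on Days 11 to 21 and ends on Days 22 to 25, the mean duration falls from 8.5 to 6.0 days under equal weights. This is a choice of convention. Capping at last contact (assumed Day 25) would reduce that error but would raise the mean overstatement for AEs that resolved on Days 11 to 21 from 4.3 to 7.4 days.

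**Conclusion.** The rule is wrong as written, and the point is minor. Every AE with a complete onset date after the last dose and a missing stop day receives a stop before its start, with a duration of 0 to -3 days for onset on Days 22 to 25. That result follows from the text and needs only that the onset is after the last dose; the day counts also assume a last dose on Day 21 and the usual duration formula. The cap can also place the stop in a month earlier than the one recorded, at a rate that depends on assumed AE lengths. The number of AEs with partial dates is unknown and probably small. AE counts and the primary PK conclusion are unaffected. The phase-label mismatch is a wording point only.

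**What to change.** In SAP Section 11.5.2.1, keep the present stop-day rule and add that the imputed stop date must not precede the AE start date or the first day of the recorded stop month. Add that where an imputed AE start falls after the recorded stop month, the duration is left missing.

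As a side correction, add one clause: an AE whose start is imputed to the treatment start date is classed On-Treatment and treatment emergent when its recorded month contains the treatment start date. The condition matters, because without it an AE whose recorded month ended before dosing would also be labelled On-Treatment. The Section 11.2.1 boundary can stay as it is for predose assessments.

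The cost is a few sentences of SAP text and a small change to the date-imputation code. AEs that continue past the last dose within the same month stay truncated, as they are now. Replacing the cap with last contact is not part of this fix.

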# 11.6. Appendix 6: Division of AIDS (DAIDS) Table for Grading the Severity of Adult and Pediatric Adverse Events

# 11.6.1. Laboratory Values

Laboratory abnormalities will be graded according to the DAIDS grading table Version 2.1, July 2017. Laboratory results are converted to use SI units; only the numeric part of the criteria will be used. If for a laboratory parameter there are multiple grades sharing the same criteria, the maximum grade will be used.

HEMATOLOGY				
	Grade 1	Grade 2	Grade 3	Grade 4
Absolute Lymphocyte Count, Low (cell/mm³; cells/L) > 5 years of age (not HIV infected)	600 to < 650 0.600 × 10  to < 0.650 × 10 	500 to < 600 0.500 × 10  to < 0.600 × 10 	350 to < 500 0.350 × 10  to < 0.500 × 10 	< 350 < 0.350 × 10 
Absolute Neutrophil Count, Low (cells/mm³; cells/L) > 7 days of age	800 to 1,000 0.800 × 10  to 1.000 × 10 	600 to 799 0.600 × 109 to 0.799 × 109	400 to 599 0.400 × 10  to 0.599 × 10 	< 400 < 0.400 × 10 
Hemoglobin, Low (g/dL; mmol/L)	10.0 to 10.9	9.0 to < 10.0	7.0 to < 9.0	< 7.0
≥ 13 years of age (male only)	6.19 to 6.76	5.57 to < 6.19	4.34 to < 5.57	<4.34
Hemoglobin, Low (g/dL; mmol/L)	9.5 to 10.4	8.5 to < 9.5	6.5 to < 8.5	< 6.5
≥ 13 years of age (female only)	5.88 to 6.48	5.25 to < 5.88	4.03 to < 5.25	< 4.03
Platelets, Decreased (cells/mm³; cells/L)	100,000 to < 125,000 100.000 × 10  to < 125.000 × 10 	50,000 to < 100,000 50.000 × 10  to < 100.000 × 10 	25,000 to < 50,000 25.000 × 10  to < 50.000 × 10 	< 25,000 < 25.000 × 10 
White Blood Cell, Decreased (cells/mm³; cells/L) > 7 days of age	2,000 to 2,499 2.000 × 10  to 2.499 × 10 	1,500 to 1,999 1.500 × 10  to 1.999 × 10 	1,000 to 1,499 1.000 × 10  to 1.499 × 10 	< 1,000 < 1.000 × 10 

Clinical Chemistry				
	Grade 1	Grade 2	Grade 3	Grade 4
Albumin, Low (g/dL; g/L)	3.0 to < LLN 30 to < LLN	≥ 2.0 to < 3.0 ≥ 20 to < 30	< 2.0 < 20	NA
Alkaline Phosphatase, High	1.25 to < 2.5 × ULN	2.5 to < 5.0 × ULN	5.0 to < 10.0 × ULN	≥ 10.0 × ULN
Alanine Aminotransferase, High	1.25 to < 2.5 × ULN	2.5 to < 5.0 × ULN	5.0 to < 10.0 × ULN	≥ 10.0 ULN
Amylase (Total), High	1.1 to < 1.5 × ULN	1.5 to < 3.0 × ULN	3.0 to < 5.0 × ULN	≥ 5.0 × ULN
Aspartate Aminotransferase, High	1.25 to < 2.5 × ULN	2.5 to < 5.0 × ULN	5.0 to < 10.0 × ULN	≥ 10.0 × ULN
Bicarbonate, Low (mEq/L; mmol/L)	16.0 to < LLN 16.0 to < LLN	11.0 to < 16.0 11.0 to < 16.0	8.0 to < 11.0 8.0 to < 110.	< 8.0 < 8.0
Direct Bilirubin, High > 28 days of age	NA	NA	> ULN with other signs and symptoms of hepatotoxicity	> ULN with life-threatening consequences (e.g., signs and symptoms of liver failure)
Total Bilirubin, High > 28 days of age	1.1 to < 1.6 × ULN	1.6 to < 2.6 × ULN	2.6 to < 5.0 × ULN	≥ 5.0 × ULN
Calcium, High (mg/dL; mmol/L)	10.6 to < 11.5	11.5 to < 12.5	12.5 to < 13.5	≥ 13.5
≥ 7 days of age	2.65 to < 2.88	2.88 to < 3.13	3.13 to < 3.38	≥ 3.38
Calcium, Low (mg/dL; mmol/L)	7.8 to < 8.4	7.0 to < 7.8	6.1 to < 7.0	< 6.1
≥ 7 days of age	1.95 to < 2.10	1.75 to < 1.95	1.53 to < 1.75	< 1.53
Creatine Kinase, High	3 to < 6 × ULN	6 to < 10 × ULN	10 to < 20 × ULN	≥ 20 × ULN
Creatinine, High Choose the method that selects for the higher grade	1.1 to 1.3 × ULN	> 1.3 to 1.8 × ULN OR Increase to 1.3 to < 1.5 × participant's baseline	> 1.8 to < 3.5 ULN OR Increase to 1.5 to < 2.0 × participant's baseline	≥ 3.5 × ULN OR Increase of ≥ 2.0 × participant's baseline
Glucose Fasting, High (mg/dL; mmol/L)	110 to 125 6.11 to < 6.95	> 125 to 250 6.95 to < 13.89	> 250 to 500 13.89 to < 27.75	≥ 500 ≥ 27.75
Glucose, Low (mg/dL; mmol/L)	55 to 64	40 to < 55	30 to < 40	< 30
≥ 1 month of age	3.05 to < 3.55	2.22 to < 3.05	1.67 to < 2.22	< 1.67
Lipase, High	1.1 to < 1.5 × ULN	1.5 to < 3.0 × ULN	3.0 to < 5.0 × ULN	≥ 5.0 × ULN
Cholesterol, Fasting, High (mg/dL; mmol/L) ≥ 18 years of age	200 to < 240 5.18 to < 6.19	240 to < 300 6.19 to < 7.77	≥ 300 ≥ 7.77	NA
Triglycerides, Fasting, High (mg/dL;	150 to 300	> 300 to 500	> 500 to < 1.000	> 1,000
mmol/L)	1.71 to 3.42	> 3.42 to 5.7	> 5.7 to 11.4	> 11.4
Phosphate, Low (mg/dL; mmol/L)	2.0 to < LLN	1.4 to < 2.0	1.0 to < 1.4	< 1.0
> 14 years of age	0.65 to < LLN	0.45 to < 0.65	0.32 to < 0.45	< 0.32

Clinical Chemistry					
	Grade 1	Grade 2	Grade 3	Grade 4	
Potassium, High (mEq/L; mmol/L)	5.6 to < 6.0	6.0 to < 6.5	6.5 to < 7.0	≥ 7.0	
	5.6 to < 6.0	6.0 to < 6.5	6.5 to < 7.0	≥ 7.0	
Potassium, Low (mEq/L; mmol/L)	3.0 to < 3.4	2.5 to < 3.0	2.0 to < 2.5	< 2.0	
	3.0 to < 3.4	2.5 to < 3.0	2.0 to < 2.5	< 2.0	
Codium High (mFg/L mmg/L)	146 to < 150	150 to < 154	154 to < 160	≥ 160	
Sodium, High (mEq/L; mmol/L)	146 to < 150	150 to < 154	154 to < 160	≥ 160	
Sodium, Low (mEq/L; mmol/L)	130 to < 135	125 to < 130	121 to < 125	≤ 120	
	130 to < 135	125 to < 130	121 to < 125	≤ 120	
Uric Acid, High (mEq/L; mmol/L)	7.5 to < 10.0	10.0 to < 12.0	12.0 to < 15.0	≥ 15.0	
	0.45 to < 0.59	0.59 to < 0.71	0.71 to < 0.89	≥ 0.89	

NA=not applicable; LLN = lower limit of normal; ULN=upper limit of normal.

Urinalysis					
	Grade 1	Grade 2	Grade 3	Grade 4	
Glucose/Glycosuria (random collection tested by dipstick)	Trace to 1+ or ≤ 250 mg	2+ or > 250 to ≤ 500 mg	> 2+ or > 500 mg	NA	
Protein/Proteinuria (random collection tested by dipstick)	1+	2+	3+ or higher	NA	
Red Blood Cells (RBCs)/Hematuria (not to be reported based on dipstick findings or on blood believed to be of menstrual origin)	6 to < 10 RBCs per high power field	≥ 10 RBCs per high power field	Gross, with or without clots OR with RBC casts OR intervention indicated	Life-threatening consequences	

NA=not applicable

